### 5.4.9.2 Trial Stopping Rules

The Chief Investigator and Sponsor retain the right to terminate the study. Specific circumstances that may precipitate such termination are as follows:

1. Unanticipated severe adverse event in this or other studies indicating a potential health hazard caused by the ATIMP
2. Significant protocol deviation and lack of compliance and cooperation on the part of an investigator, which endangers the safety of the participants or the validity of the study
3. Death of a participant at any time point after ATIMP administration that is possibly, probably, or definitely related to the ATIMP
4. The occurrence of a non-ocular malignancy at any point after gene transfer that is possibly, probably, or definitely related to the ATIMP

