**Gene Therapy for Achromatopsia (CNGA3)**

	
 
• Participated in another research study involving an investigational therapy for ocular disease within the last 6 months
 
• Use of high dose regular non-steroidal anti-inflammatory drugs at the time of screening
 
• Have any other condition that the Principal Investigator (PI) considers makes them inappropriate for entry into the trial
 
• Are unwilling to consider the possibility of entry into a subsequent longer term follow up study
 
• During the 6 weeks prior to baseline, have had any confirmed SARS-CoV-2 (COVID-19) infection
 

Study Type	Phase I/II, open-label, non-randomised, multi-centre, dose escalation study, followed by dose confirmation in children with Achromatopsia owing to defects in CNGA3
Date of First Enrolment	Anticipated Q1 2019
Target Sample Size	Up to 18 participants
Primary Outcome(s)	
The primary outcome is safety of subretinal administration of AAV8-hG1.7p.coCNGA3.
 
Safety is defined as the absence of ATIMP-related:
 
 
• Reduction in visual acuity by 15 ETDRS letters or more that fails to resolve to within 15 letters of baseline in a 4-week period once prophylactic treatment commences
 
• Severe unresponsive inflammation
 
• Infective endophthalmitis
 
• Ocular malignancy
 
• Grade III or above non-ocular SUSAR
 
 
Safety will be assessed for 6 months after the intervention in this study, and a further optional 4.5 years in a separate subsequent study.

Key Secondary Outcomes	
The secondary outcomes are measures of the efficacy of the intervention, which will be performed on an individual participant basis and will be descriptive in nature. Efficacy will be assessed at several time points between 3 to 6 months after the intervention:
 
 
1) Any improvement in visual function from baseline that is greater than the baseline variation for that test and is sustained for at least two consecutive assessments.
 
2) Any improvement in retinal function from pre-intervention that is greater than the baseline variation and measurable by electroretinography (ERG).
 
3) Quality of life measures including EQ-5D and IVI or equivalent as appropriate.
 

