## 4.2 Objectives

### 4.2.1 Primary Objective

The primary research objective is to assess the safety of an AAV2/8 vector for *hCNGA3* gene replacement in the retina. Safety is defined as:

Safety is defined as the absence of an ATIMP-related:

- Reduction in visual acuity by 15 ETDRS letters or more that fails to resolve to within 15 letters of baseline in a 4-week period once prophylactic treatment commences
- Severe unresponsive inflammation (defined below)
- Infective endophthalmitis
- Ocular malignancy
- Grade III or above non-ocular SUSAR (see section 5.11.3)

Severe unresponsive inflammation will be defined according to the Standardisation of Uveitis Nomenclature (SUN) Working Group grading system (Jabs *et Al.* 2005) i.e.

- anterior chamber cells 3+ (26-50 cells in a field size of 1mm x 1-mm slit-beam), or
- anterior chamber flare 3+ (marked, iris and lens details hazy), or
- vitreous haze 3+ (Ophthalmology 1985; 92:467-71)

that fails to improve by 2 steps (or to grade 0) during a 6-week period.

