#### 4.3.2.1 Dose escalation criteria and Dose Limiting Events

Dose escalation will be managed according to review of available and emerging data on the subjects administered ATIMP top date and the occurrence, if any, of DLE's or medically important events. An SDMC will review data from a minimum of 6 weeks of follow up from each cohort of participants (at least one older child, 11-15 years of age per cohort), before recommending the next dose to be assessed in a further cohort of participants or to additional participants at the same dose level.

A DLE is defined as any of the below occurring during the 6 weeks following administration, at least possibly related to the ATIMP, not surgery alone:

- A reduction in visual acuity by 15 ETDRS letters or more that fails to resolve to within 15 letters of baseline in a 4-week period once prophylactic treatment commences
- Severe unresponsive inflammation (defined below)\*
- Infective endophthalmitis
- Ocular malignancy
- Grade III or above non-ocular SUSAR (see section 5.11.3)

\* Severe unresponsive inflammation will be defined according to the Standardisation of Uveitis Nomenclature (SUN) Working Group grading system (Jabs *et Al.* 2005) i.e.

- anterior chamber cells 3+ (26-50 cells in a field size of 1mm x 1-mm slit-beam), or
- anterior chamber flare 3+ (marked, iris and lens details hazy), or
- vitreous haze 3+ (Ophthalmology 1985; 92:467-71)

that fails to improve by 2 steps (or to grade 0) during a 6-week period.

Review of safety data will be undertaken by the SDMC prior to each dose escalation.

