## 5.5 Outcomes

### 5.5.1 Primary Outcomes

The primary outcome is defined as any of the below occurring during the 6 weeks following administration, at least possibly related to the ATIMP, not surgery alone:

- Reduction in visual acuity by 15 ETDRS letters or more that fails to resolve to within 15 letters of baseline in a 4-week period once prophylactic treatment commences
- Severe unresponsive inflammation
- Infective endophthalmitis
- Ocular malignancy
- Grade III or above non-ocular SUSAR (see section 5.11.3)

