#### **5.10.3.2 Statistical Methods – Primary Outcome Analysis**

The primary outcome is safety of subretinal administration of the ATIMP defined as any of the below occurring during the 6 weeks following administration, at least possibly related to the ATIMP, not surgery alone:

- Reduction in visual acuity by 15 ETDRS letters or more that fails to resolve to within 15 letters of baseline in a 4-week period once prophylactic treatment commences
- Severe unresponsive inflammation
- Infective endophthalmitis
- Ocular malignancy
- Grade III or above non-ocular SUSAR (see section 5.11.3)

The number of DLEs at each dose level will be summarised by cohort and overall.

It is anticipated that the ATIMP will be administered at the MTD in up to 18 participants. Safety data relating to these participants will allow estimation of an upper bound for the true event rate through a 95% confidence interval.

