#### 2. OUTCOME DEFINITIONS

### 2.1. Primary Safety Outcome

The primary safety outcome is defined as the absence/presence of any of the below events occurring during the 6 weeks following administration, at least possibly related to the ATIMP, not surgery alone:

- Reduction in visual acuity by 15 Early Treatment Diabetic Retinopathy Study (ETDRS) letters or more
- Severe unresponsive inflammation (defined in Section 4.2 of the protocol)

- Infective endophthalmitis
- Ocular malignancy
- Grade III or above non-ocular suspected unexpected serious adverse reaction (SUSAR) (Protocol MGT006, Section 5.11.3.4.2 Severity or Grading of Adverse Events).

This is the same criteria as the dose limiting event in the dose escalation phase.

Overall safety will be assessed for 6 months after the intervention in this study, and a further 4.5 years in a separate long-term follow-up study (Protocol MGT007).

The adverse events preferred terms are identified in Attachment 2.

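### The primary safety proportion stops at week 6, although the trial summary ties the same five-component safety definition to 6 months of assessment and the primary objective sets no window

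*Protocol*

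**What the plan says.** **Definitions without a 6-week limit.** The Primary Outcome(s) row of Protocol 1.3 lists five ATIMP-related events: a 15-letter acuity loss that does not resolve, severe unresponsive inflammation, infective endophthalmitis, ocular malignancy, and a non-ocular SUSAR of Grade III or above. The row closes with "Safety will be assessed for 6 months after the intervention in this study". Protocol 4.2.1 repeats the list as the primary objective, introduced by "Safety is defined as the absence of an ATIMP-related", with no window.

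**Definitions with a 6-week limit.**
- Protocol 5.5.1: "The primary outcome is defined as any of the below occurring during the 6 weeks following administration".
- Protocol 5.10.3.2: "The primary outcome is safety of subretinal administration of the ATIMP defined as any of the below occurring during the 6 weeks following administration".
- SAP 2.1: "the absence/presence of any of the below events occurring during the 6 weeks following administration". It adds that these are the dose-limiting event criteria, and says separately that overall safety is assessed for 6 months.
- Protocol 4.3.2.1, for dose escalation: "A DLE is defined as any of the below occurring during the 6 weeks following administration".

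**Planned analysis.** SAP 5.1 gives the proportion with the primary safety outcome, with a 95% interval, by age group, dose level and overall. No such proportion is planned for any longer period.

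**Termination list.** Item 4 of Protocol 5.4.9.2 reads "The occurrence of a non-ocular malignancy at any point after gene transfer", provided it is at least possibly related to the ATIMP. Ocular malignancy is not named. Item 1 is general: an unanticipated severe event pointing to a hazard from the product, with no limit on time or organ.

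**The concern.** The primary safety result is the one number from this trial that carries an interval for harm. A reader of the trial summary would take it to cover 6 months. As the SAP stands it covers 6 weeks, and an event on the five-item list first seen at the week 12 or week 24 visit leaves it unchanged. The headline could read zero events in a trial where one of the listed events had occurred and had been judged related.

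Two features of the protocol make this more than a matter of labels. Protocol 5.11.3.5.4 explains the primary criterion as the absence of an event with a substantial and sustained effect on vision, and accepts surgery-related acuity loss for up to 8 weeks. The first scheduled visit beyond 8 weeks is week 12, which is outside the window. And Protocol 4.1.5.3 relies on the monitoring in 5.4.2.3, which runs to 6 months, to detect an intraocular tumour early. A tumour found by that monitoring after week 6 would not count in the primary outcome.

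The termination list raises a separate question of wording: the malignancy in the safety definition is ocular, and the malignancy in the list is non-ocular.

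**Working it through.** The plan states no figure to reproduce; Protocol 5.7 says there is no formal sample size calculation. The check compares passages and adds simple arithmetic.

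**1. Windows side by side**

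| Place | Five-event list | Window |
|---|---|---|
| Protocol 1.3, Primary Outcome(s) | yes | safety assessed for 6 months |
| Protocol 4.2.1 | yes | none |
| Protocol 4.3.2.1 (DLE) | yes | 6 weeks |
| Protocol 5.5.1 | yes | 6 weeks |
| Protocol 5.10.3.2 | yes | 6 weeks |
| SAP 2.1 | yes | 6 weeks; overall safety 6 months |
| SAP 5.1 (proportion and interval) | by reference to SAP 2.1 | 6 weeks |

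**2. Share of follow-up inside the window.** SAP Table 1 sets target days 43 for week 6 and 169 for week 24, with the day of administration as day 1.
- Window: 43 − 1 = 42 days. Follow-up: 169 − 1 = 168 days.
- 42/168 = 25%, so 75% of follow-up to week 24 lies outside.
- If 6 months is taken as 183 days (an assumption), 42/183 = 23%, so 77% lies outside.

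**3. What one late event would do (illustration).** Suppose 18 participants are dosed, the stated maximum, and one has a related qualifying event first seen at week 12.
- Overall: 0/18 = 0% to week 6, against 1/18 = 5.6% to week 24.
- In a dose cohort of 3: 0/3 = 0%, against 1/3 = 33%.

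**4. Where a late event would still be seen**
- SAP 5.2 tabulates all treatment-emergent adverse events and serious events, by severity and by relationship to the ATIMP, with no 6-week cut.
- SAP 6.1 summarises each efficacy outcome by time point and plots individual data; SAP 2.2 includes visual acuity among those outcomes.
- Protocol 5.11.3.5.4 treats any related serious event as a SUSAR, because nothing is expected for the product.
- Escalation review (Protocol 4.3.2.1, 4.3.2.2.2 and 4.3.2.2.3) also weighs other important or clinically relevant events.
- The SDMC (Protocol 5.11.4.4.2) reviews accumulating data and advises on continuation.
- In Protocol 5.4.9.2, item 1 and the general right to terminate have no time limit.

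So a late event is visible and can be acted on. It is missing from one place: the primary proportion and its interval.

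**5. Termination list against the safety definition.** Ocular malignancy is in Protocol 4.2.1 and absent from item 4. Only item 1 could take it in, and that depends on whether it is unanticipated. Protocol 4.1.5.3 discusses an intraocular tumour as a recognised, highly unlikely risk, whereas 5.11.3.5.4 says no event is expected for the ATIMP. Coverage is therefore a matter of interpretation.

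**6. Data needed for a week 24 figure.** Protocol Table 2 schedules visual acuity, ocular examination and adverse event review at both week 12 and week 24.

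**The case against.** The operative definitions agree with one another: Protocol 4.3.2.1, 5.5.1, 5.10.3.2 and SAP 2.1 all say 6 weeks, and SAP 2.1 equates the primary outcome with the DLE. The window looks deliberate. An objective stated without a window, as in 4.2.1, is normally made operational by the outcome section. The 6-month sentence in 1.3 can be read as the length of safety monitoring, which is how SAP 2.1 treats it. This largely stands for 4.2.1. It is weaker for 1.3, where the sentence sits in the primary outcome row directly below the five events.

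Calendar share is also not a measure of bias. Of the eight scheduled post-dose visits, six (day 1, day 3, weeks 1, 2, 4 and 6) fall in the window, so 6/8 = 75% of examinations count. That is fair: the 25% describes time covered, not the proportion of events missed, and the documents give no basis for estimating the latter.

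The analysis is descriptive, with no hypothesis test, and late events are tabulated elsewhere. That is true, but those tables do not give the five-component proportion with an interval.

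A reader might infer that an ocular malignancy after week 6 counts in no decision. The documents do not support that: the SDMC, the escalation reviews, termination item 1 and the general right to terminate can all take it in. Item 4 is itself discretionary, since the list gives circumstances that may lead to termination, so leaving ocular malignancy out removes no mandatory stop. A reader might also infer that a malignancy component limited to 6 weeks could hardly ever be observed. The documents give no figure on tumour latency, so that cannot be asserted from them.

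**Conclusion.** The point holds as an inconsistency in the primary safety definition and a gap in the planned analysis. Protocol 1.3 attaches 6 months to the five-event definition and 4.2.1 attaches no limit, while the only planned proportion with an interval covers 6 weeks, or 25% of follow-up to week 24 (23% on a 183-day reading of 6 months). A related qualifying event first seen at week 12 or 24 would be reported and could be acted on, but would leave the primary safety proportion unchanged. With 18 dosed, each participant so affected is worth 5.6 percentage points overall. This assumes that SAP 5.1 is followed as written and that the week 12 and week 24 visits take place as scheduled.

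The ocular versus non-ocular wording in Protocol 5.4.9.2 is a separate and smaller matter: an unexplained mismatch with 4.2.1, not evidence that a late ocular malignancy would be ignored.

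**What to change.** 1. Leave the 6-week DLE figure in place for escalation. In SAP 5.1, add the same five-component proportion with its interval through week 24, by age group, dose level and overall, beside the 6-week figure. State whether onset or completion of a criterion must fall in the window: the inflammation criterion itself takes 6 weeks to be met, and an acuity loss first seen at week 24 has no later scheduled visit at which to judge resolution.
2. Reconcile Protocol 1.3 and 4.2.1 with 5.5.1, 5.10.3.2 and SAP 2.1, so that each says which window defines the primary outcome and which describes overall safety.
3. Reconcile Protocol 5.4.9.2 with the safety definition in 4.2.1 on ocular and non-ocular malignancy. This is for the sponsor and investigators to settle; no stopping rule is proposed here.

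The cost is one additional table from data already scheduled at weeks 12 and 24, plus wording changes. The reported safety rate may be somewhat less favourable.

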## 5.5 Outcomes

### 5.5.1 Primary Outcomes

The primary outcome is defined as any of the below occurring during the 6 weeks following administration, at least possibly related to the ATIMP, not surgery alone:

- Reduction in visual acuity by 15 ETDRS letters or more that fails to resolve to within 15 letters of baseline in a 4-week period once prophylactic treatment commences
- Severe unresponsive inflammation
- Infective endophthalmitis
- Ocular malignancy
- Grade III or above non-ocular SUSAR (see section 5.11.3)

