#### ***4.1.5.6 Risk of adverse effects of corticosteroids***

Candidates will be screened for contra-indications to transient immune suppression by corticosteroids; in particular, a history of uncontrolled hypertension, diabetes mellitus, tuberculosis, renal impairment, osteoporosis, gastric ulceration, severe affective disorder immunocompromised status and increased risk of infections. Possible adverse effects of short-term systemic corticosteroid use include increases in blood pressure and blood sugar, weight gain, changes in mood or behaviour, increased risk of infections, increased intraocular pressure and cataracts. Local steroids used on or near the eye can cause increased intraocular pressure and cataracts. The possibility of steroid-induced adverse effects will be monitored regularly. In particular, blood pressure and blood glucose will be measured, as will renal function and liver function (at baseline, 1 day, 7 days, 2 weeks and 4 weeks after surgery). Common and expected laboratory findings observed in the other ongoing studies utilising prophylactic corticosteroids have included but are not limited to: leucocytosis, neutrophilia, hyperglycaemia. If the latter should occur, then a referral to a diabetologist would occur. On occasion

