### 4.3.2.2.5 Additional considerations

In the event of a DLE in one of the participants at a given dose, the cohort may be expanded at the same dose level. The SDMC will review the safety data and recommend that additional participants may be treated at this dose. The SDMC may recommend that the same dose of ATIMP is administered to additional participants. The dose escalation will continue until SDMC are comfortable on review of the accumulating data, to recommend a maximum dose to be administered, or 3 participants have been administered the highest dose without any DLEs, or until at least 2 participants among a cohort of 3 to 6 participants experience DLEs (i.e.,  $\geq 33\%$  of patients with a DLE at that dose level), in which case the recommended dose will be the level below this dose. In the event that 1 or 2 DLEs are seen at the first dose level, the SDMC may recommend administering a lower dose to that described in the protocol to a cohort of participants.

Table 1: Dose escalation table

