## Gene Therapy for Achromatopsia (CNGA3)

---

7. Prednisolone or Prednisone (oral steroid) as prophylaxis against potential intraocular immune responses:

- 0.5 mg/kg daily for one week **prior** to ATIMP administration
- 1mg/kg daily for the first week following ATIMP administration
- 0.5mg/kg daily for the second week following ATIMP administration
- 0.25mg/kg daily for the third week following ATIMP administration
- 0.125mg/kg daily for the fourth week following ATIMP administration

All Non- Investigational Medicinal Products (NIMPs) are licensed within the EU and US and will be procured from standard hospital stock.

Sites will maintain a system that allows adequate reconstruction of NIMP movements and permits recording of which participants received which NIMPs during the trial, with an evaluation of the compliance where necessary.

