#### **5.4.2.2.1 Pre-operative Procedures**

For prophylaxis against potential intraocular immune responses to the ATIMP, participants will be prescribed a course of oral prednisolone as described in section 5.4.1.5.

Preoperative procedures and intraocular administration of ATIMP will be as described in the Gene Therapy for Achromatopsia (*CNGA3*) study manual.

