Following intraocular administration of ATIMP, the retinal periphery will be examined for any unplanned retinal breaks for appropriate management by retinopexy with or without intraocular tamponade at the discretion of the operating surgeon. Intraocular instruments used subsequent to ATIMP delivery are disposable and will be destroyed after a single use. Sclerotomies may be secured using a vicryl suture. Standard doses of cefuroxime antibiotic and betamethasone will be administered subconjunctivally as prophylaxis against postoperative infection and inflammation respectively. Bupivacaine will be administered for analgesia. The surgical procedure may be modified on a case-by-case basis in the interests of safety; any modification will be documented in the operation notes and CRF.

On the basis of our own experience, we anticipate that the subretinal ATIMP bleb will resolve spontaneously during the first 48 hours.

Surgery may be performed, as is conventional for intra-ocular procedures, on a day-case basis and participants will be managed subsequently as out-patients, although hospital-based accommodation may be used for convenience.

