### **(i) Clinical assessment of intraocular inflammation**

The degree of intraocular inflammation will be assessed by slit-lamp biomicroscopy at each time point. A temporary intraocular inflammatory response is expected following vitrectomy surgery. This is typically evident clinically on slit-lamp biomicroscopy as 'flare' and cells in the anterior chamber and can be of moderate (2+ cells) intensity. The degree of intraocular inflammation is expected to decline over the course of the first 4 weeks following the surgical procedure, at which time the routine topical and systemic immunosuppression will be discontinued. Prolonged or severe intraocular inflammation, or deterioration in visual acuity that may be related to intraocular inflammation, will be investigated and managed conventionally with further topical and/or systemic immunosuppression.

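### SAP 2.1 omits the recovery clause from the visual acuity criterion yet calls its criteria the same as the DLE, and the protocol's own clause starts the 4 weeks from the wrong kind of treatment

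*Protocol*

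**What the plan says.** Protocol 5.5.1 defines the primary outcome as any of five kinds of event within 6 weeks of administration that are at least possibly related to the ATIMP and not to surgery alone. The acuity event is a loss of 15 or more ETDRS letters that "fails to resolve to within 15 letters of baseline in a 4-week period once prophylactic treatment commences". The same clause appears in 1.3, 4.2.1, 4.3.2.1 (the DLE definition) and 5.10.3.2. The last of these adds: "The number of DLEs at each dose level will be summarised by cohort and overall". Under 4.3.2.2.5, escalation may continue "until at least 2 participants among a cohort of 3 to 6 participants experience DLEs", in which case the recommended dose is the level below.

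SAP 2.1 gives the acuity event as a loss of 15 or more letters and stops there. It then says that the criteria are the same as those of the dose-limiting event. Its inflammation item refers back to the protocol for a definition; its acuity item does not. SAP 5.1 reports the proportion with the primary outcome and a 95% confidence interval by age group, dose level and overall.

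The protocol does not define the treatment that starts the 4 weeks. Elsewhere in the available text, related words describe scheduled perioperative drugs:

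- 5.4.1.5: "Prednisolone or Prednisone (oral steroid) as prophylaxis against potential intraocular immune responses", starting one week before surgery and tapering through week 4.
- 5.4.2.2.1: "For prophylaxis against potential intraocular immune responses to the ATIMP, participants will be prescribed a course of oral prednisolone".
- 5.4.2.2.2: "Standard doses of cefuroxime antibiotic and betamethasone will be administered subconjunctivally as prophylaxis against postoperative infection and inflammation respectively".
- 4.1.5.6, on laboratory findings "observed in the other ongoing studies utilising prophylactic corticosteroids".

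Treatment given in response to a loss is described differently. Section 5.4.2.3 (i) says that "deterioration in visual acuity that may be related to intraocular inflammation, will be investigated and managed conventionally with further topical and/or systemic immunosuppression".

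**The concern.** There are two separate faults.

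The first is a mismatch between the documents. The SAP and the protocol would report different numbers for what the SAP says is one definition. The SAP version also departs from the protocol's stated reasoning: 5.11.3.5.4 explains that a temporary fall in acuity is expected after intraocular surgery, and for that reason ties the safety outcome to a lasting effect on vision. A count that includes recovered losses does not measure that.

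The second is the start of the recovery period. If the clause means the perioperative drugs, the 4 weeks run from a fixed date near surgery and not from the loss, so a late loss has little or no time to recover. Taken literally, such a loss could be called never an event (it was absent during the 4 weeks) or an event at once (it cannot resolve within them). The label feeds the DLE count by dose and the two-DLE rule. In cohort 1, the release of two more children after the first is also worded on the absence of a DLE alone.

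**Working it through.** **1. Mismatch.** Set side by side:

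| | Loss of 15+ letters, ATIMP-related, within 6 weeks | Must also fail to recover in 4 weeks |
|---|---|---|
| Protocol 4.3.2.1, 5.5.1, 5.10.3.2 | yes | yes |
| SAP 2.1 | yes | not stated |

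Every acuity event under the protocol is also one under the SAP, but not the reverse, so the SAP count can only be equal or higher. Example: in a cohort of 3, one participant has an ATIMP-related loss at D1 that recovers by W2, and nothing else occurs.

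- SAP primary outcome: 1/3 = 33%.
- Protocol DLEs: 0/3 = 0%.

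**2. Start of the 4 weeks.** Inputs: acuity visits at days 1, 3, 7, 14, 28 and 42 within the 6-week window (protocol 5.4.2.3 (iv) and Table 2); a 28-day recovery period; surgery on day 0.

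The SAP numbers days from 1 at administration, so its target day is 7 × week + 1: week 4 gives 29 and week 6 gives 43. Both match SAP Table 1 and correspond to days 28 and 42 after administration.

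Days left to recover = (start + 28) − visit day, where zero or less means none:

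| First seen | Start day 0 (ends day 28) | Start day −7 (ends day 21) |
|---|---|---|
| D1 | 27 | 20 |
| D3 | 25 | 18 |
| W1 | 21 | 14 |
| W2 | 14 | 7 |
| W4 | 0 | none (−7) |
| W6 | none (−14) | none (−21) |

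Day 0 is the date of the end-of-surgery drugs. Day −7 is the start of the oral steroid and is a strained reading. Visit windows change little: W4 may be held on days 21 to 35, so an early visit with a day 0 start leaves at most 28 − 21 = 7 days. W6 may be held on days 35 to 49 and never leaves any. Two of the six in-window visits therefore have no recovery time at target days.

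**3. What the label could change.** Suppose a cohort of 3 has one clear DLE and one ATIMP-related loss first seen at W6. The two literal readings give 1 of 3 (33%) or 2 of 3 (67%). One DLE allows expansion at the same dose; two put the recommended dose one level down.

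**4. If the 4 weeks start with the loss** (treatment assumed to begin at the visit where it is seen), they end on day 14 + 28 = 42 for W2, 28 + 28 = 56 for W4 and 42 + 28 = 70 for W6. The last two fall after the 6-week review. The next scheduled acuity visit, W12, may be held from day 84 − 14 = 70.

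**The case against.** The best defence of the protocol wording is that a loss failing to resolve after treatment starts most naturally means treatment begun for the loss. Section 5.4.2.3 (i) provides such treatment. On that reading, losses at W4 and W6 do get four weeks, and the fault is one wrong adjective. The exact phrase occurs only inside the criterion; it is the related words that name perioperative drugs. Section 4.1.5.1, on immune responses, was not available and may explain it, and the study manual and SDMC charter were not seen either. All of this stands, and it makes the second fault smaller than the literal arithmetic suggests. It does not remove the need for a correction. Section 5.4.2.3 (i) covers only loss that may be due to inflammation. Treatment for raised pressure or retinal detachment is described elsewhere, but a loss that receives no treatment has no start date.

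For the SAP, it can be said that the sentence asserting sameness points back to the DLE, that the omission errs towards counting more events, and that the analysis is descriptive with events listed. These limit the harm. The SAP still contradicts itself, and its reported proportion depends on which sentence is followed.

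A reader might infer that late losses would escape review, or that a dose decision would turn on the wording alone. The documents do not support that. The SDMC reviews safety data before each escalation; escalation is managed on medically important events as well as DLEs; cohorts 2 and 3 add other clinically relevant events; and the 6 weeks are a minimum.

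**Conclusion.** The point holds in two parts of unequal strength.

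- **SAP mismatch: firm.** It rests on the text alone. A recovered ATIMP-related loss is a primary event in the SAP and not a DLE in the protocol, for example 1 of 3 against 0 of 3.
- **Start of the 4 weeks: a wording defect, with moderate confidence.** The zero recovery time at W4 and W6 holds only on the literal day 0 (or day −7) reading, at target days, and on the text available. It should not be read as showing that the sponsor meant late losses to have no recovery time. The likelier intent is treatment for the loss.

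The SAP proportion as now written does not depend on this start date, because it uses no recovery clause; once the clause is added, it will. Severity is minor to moderate: the effect is on how events and DLEs are classified, not on whether losses are seen.

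**What to change.** 1. **SAP 2.1:** add the recovery clause so that the acuity item matches the DLE. Also list every ATIMP-related loss of 15 or more letters within 6 weeks, recovered or not, so that the stricter count is kept. Since Attachment 2 identifies the acuity event only by a preferred term, say that recovery is judged from the acuity measurements.
2. **Protocol 1.3, 4.2.1, 4.3.2.1, 5.5.1 and 5.10.3.2:** replace the end of the clause, from the word *once* on, with: *from the start of treatment for the loss, or from the visit at which the loss is first recorded if no treatment is given*. This keeps the condition that treatment has been tried and covers untreated loss.
3. **6-week review:** state that a loss whose 4 weeks have not elapsed is reported to the SDMC as unresolved.

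The cost is one phrase in five protocol places, one clause and one listing in the SAP with a line on derivation, and one sentence on the review. No scheduled visit is added. The downside is that a few late losses are classified finally only after the 6-week review: the 4 weeks end on day 56 for a loss first seen at W4 and day 70 for one at W6, or later if treatment starts after the visit.
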